### **9.3.5. Other Safety Analyses**

All safety analyses will be performed on the safety population.

AEs, BP, PR, and safety laboratory data will be reviewed and summarized on an ongoing basis during the study to evaluate the safety of participants. Any clinical laboratory, BP, and PR abnormalities of potential clinical concern will be described. Safety data will be presented in tabular and/or graphical format and summarized descriptively, where appropriate.

Medical history and physical examination collected during the course of the study will be considered source data and will not be required to be reported, unless otherwise noted. However, any untoward findings identified on physical and/or neurological examinations conducted during the active collection period will be captured as AEs, if those findings meet the definition of an AE. Data collected at screening that are used for inclusion/exclusion criteria, such as laboratory data, and vital signs, will be considered source data, and will not be required to be reported, unless otherwise noted. Demographic data collected at screening will be reported.

### **9.4. Interim Analyses**

No interim analysis will be conducted for this study. As this is an open-label, unblinded study, the sponsor may conduct reviews of the data during the study for the purpose of safety assessment, facilitating PK/PD modeling, and/or supporting clinical development.

### **9.5. Sample Size Determination**

The sample size of 12 evaluable participants per cohort is considered to provide a suitable estimate of precision of PK parameters of PF-07321332 (nirmatrelvir) in severe renal impairment participants on HD and not on HD, as this provided 40% precision (the width of

90% confidence interval) for  $AUC_{inf}$  and  $C_{max}$ . To ensure sufficient PK data for analysis, any participant with insufficient PK samples for analysis may be replaced.

To identify an adequate sample size for the PK, we assessed the precision of estimating the PK parameter using different sample sizes, as defined by the width of the resultant confidence intervals represented as a percentage of the mean value of the PK parameter. Currently, no PK data is available in severe renal impairment following multiple doses of PF-07321332 (nirmatrelvir); therefore, we used single dose PK data of PF-07321332 (nirmatrelvir) in severe renal impairment adults not on dialysis (Table 1) to determine the CV estimates for PF-07321332 (nirmatrelvir) PK parameters. As illustrated in Table 1, the CV estimates for PF-07321332 (nirmatrelvir)  $AUC_{inf}$  and  $C_{max}$  range from 33% to 38% (ie, 0.33 to 0.38).

**Table 1. PF-07321332 (nirmatrelvir) PK Parameters Following Single Dose of PF-07321332 (nirmatrelvir)/Ritonavir 100 mg/100 mg in Severe Renal Impairment Patients**

PK Parameter (units)	PF-07321332 (nirmatrelvir) (N=8)
$C_{max}$ (ng/mL)	2369 (38)
$AUC_{inf}$ (ng*hr/mL)	44040 (33)
$T_{max}$ (hr)	3.00 (1.00-6.05)
$t_{1/2}$ (hr)	13.37 ± 3.3225

Values are presented as geometric mean (geometric % CV) except median (range) for  $T_{max}$  and arithmetic mean ± SD for  $t_{1/2}$ .

Since we anticipate that study participants may experience more variability in PK parameters than the available data given the wider range of multiple doses, precision is described with an anticipated CV of 0.2, 0.3, or 0.4.

Table 2 below shows the upper and lower confidence limits and 90% CI width for the mean PK parameter (eg,  $AUC$ ,  $t_{1/2}$ , or  $C_{max}$ ), presented as a percentage of the mean, for different N and CV. With a sample size of 12 evaluable patients and a CV equal to 0.4, the 90% CI will range from 79.3% – 120.7 % of the mean, and the corresponding CI width will be 41.4% of the mean. This rather tight CI would indicate whether or not the study findings reveal a higher than 40% difference from the PK parameter in a severe renal impaired population.

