2.4. Sample Size Determination

The 12 evaluable participants per cohort is considered sufficient to provide a suitable estimate of precision of PK parameters of nirmatrelvir in severe renal impairment participants on HD and not on HD, in which provides approximately 40% precision (the width of 90% confidence interval) for AUC_{inf} and C_{max} . To ensure sufficient PK data for analysis, any participant with insufficient PK samples for analysis may be replaced.

To identify an adequate sample size for PK, we assessed the precision of estimating the PK parameter using different sample sizes, as defined by the width of the resultant confidence intervals represented as a percentage of the mean value of the PK parameter. Currently, no PK data is available in severe renal impairment following multiple doses of nirmatrelvir; therefore, a single dose PK data of nirmatrelvir in severe renal impairment adults not on dialysis (Table 3) was used to determine the CV estimates for nirmatrelvir PK parameters. The CV estimates in Table 3, for nirmatrelvir AUC_{inf} and C_{max} range from 33% to 38% (ie, 0.33 to 0.38).

Table 3. PF-07321332 (nirmatrelvir) PK Parameters Following Single Dose of PF-07321332 (nirmatrelvir) /Ritonavir 100 mg/100 mg in Severe Renal Impairment Patients

PK Parameter (units)	Nirmatrelvir (N=8)
C_{max} (ng/mL)	2369 (38)
AUC_{inf} (ng*hr/mL)	44040 (33)
T_{max} (hr)	3.00 (1.00-6.05)
$t_{1/2}$ (hr)	13.37 ± 3.3225

Values are presented as geometric mean (geometric % CV) except median (range) for T_{max} and arithmetic mean ± SD for $t_{1/2}$.

The study participants may experience more variability in PK parameters than the available data given the wider range of multiple doses, thus a precision is described with an anticipated CV of 0.2, 0.3, or 0.4.

Table 4 below shows the upper and lower confidence limits and 90% CI width for the mean PK parameter (eg, AUC , $t_{1/2}$, or C_{max}), presented as a percentage of the mean, for different N and CV. With a sample size of 12 evaluable participants and a CV equal to 0.4, the 90% CI will range from 79.3% – 120.7 % of the mean, and the corresponding CI width will be 41.4% of the mean. The PK parameter will be estimated with a tight 95% CI in the a severe renal impaired population.

Table 4. Percentile Range and Width of 90% Confidence Intervals for the Mean PK Parameter

N	CV=0.2		CV=0.3		CV=0.4	
	Range	Width	Range	Width	Range	Width
8	86.6-113.4%	26.8%	79.9-120.1%	40.2%	73.2-126.8%	53.6%

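### Protocol 9.5 turns the full width of a one-sample 90% CI into an ability to say whether exposure differs by more than 40%, which does not follow

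*Protocol*

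**What the plan says.** Protocol 9.5 bases the sample size on precision, "as defined by the width of the resultant confidence intervals represented as a percentage of the mean value of the PK parameter". So precision here means the whole width of the interval, not the distance from the mean to a limit.

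- The planning case: "With a sample size of 12 evaluable patients and a CV equal to 0.4", "the 90% CI will range from 79.3% – 120.7 % of the mean". The width is given as 41.4%.
- The next sentence calls this interval rather tight and says it "would indicate whether or not the study findings reveal a higher than 40% difference from the PK parameter in a severe renal impaired population".
- The single-dose data in Table 1 (N=8, severe impairment, not on dialysis) are cited as the source of the CV, which was 33% for AUCinf and 38% for Cmax. They are not named as a comparator.
- Protocol 9.1 says that there are no treatment comparisons and that all analyses are descriptive. SAP 5.1 adds that there are no hypotheses and no formal decision rules.
- SAP 2.4 repeats the table and states that "the corresponding CI width will be 41.4% of the mean". It omits the sentence about a 40% difference. In its place it says that the parameter will be estimated with a tight 95% CI, although the table and the text before it are at 90%.

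**The concern.** The only 40% figure in the argument is the width of the interval. A width of about 40% does not mean that the interval can settle whether a difference exceeds 40%. For that, the interval for the ratio to a stated reference must lie wholly on one side of the 40% line. Whether it does depends on the observed ratio, the scale and the uncertainty of the reference, and the section gives none of these.

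PK is the secondary objective, and this sentence is where the protocol tells the reader what 12 participants per cohort can conclude about exposure. A reader who takes it at face value could treat a middling result, say 30% above earlier data, as showing no difference above 40%, when the interval would still include one.

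**Working it through.** **Inputs (Protocol 9.5).** n = 12 per cohort, CV = 0.4, two-sided 90% confidence, difference of interest 40%.

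**1. Reproduce the plan's figure.** One-sample t interval as a percentage of the mean: 100 ± 100 × t(0.95, n−1) × CV/√n.

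- t(0.95, 11) = 1.796, so the half-width is 1.796 × 0.4/√12 = 0.207, or 20.7%.
- Limits are 79.3% and 120.7%. The width is 41.5% unrounded, or 41.4% from the rounded limits.
- The other cells of Table 2 also reproduce, to within about 0.2 percentage points. The table is correct.

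**2. When does this interval settle the 40% question?** Assume the most favourable case, a reference known without error, and let R be the observed ratio of the cohort mean to it. With the protocol's own interval, the limits for the ratio are 0.793R and 1.207R.

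- Show an increase above 40%: 0.793R ≥ 1.4, so R ≥ 1.4/0.793 = 1.77.
- Exclude an increase above 40%: 1.207R ≤ 1.4, so R ≤ 1.4/1.207 = 1.16.
- Show a decrease above 40%: 1.207R ≤ 0.6, so R ≤ 0.50.
- Exclude a decrease above 40%: 0.793R ≥ 0.6, so R ≥ 0.76.

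**3. Same check on the log scale.** SD = √ln(1 + 0.4²) = 0.385. The half-width is 1.796 × 0.385/√12 = 0.200, a factor of e^0.200 = 1.22.

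| Scale | Excludes an increase >40% | Undecided | Shows an increase >40% |
|---|---|---|---|
| Protocol's interval, percentage of observed mean | R ≤ 1.16 | 1.16 to 1.77 | R ≥ 1.77 |
| Log scale | R ≤ 1.15 | 1.15 to 1.71 | R ≥ 1.71 |
| Additive, SD fixed at 40% of the reference (1.4 ± 0.207) | R ≤ 1.19 | 1.19 to 1.61 | R ≥ 1.61 |

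The undecided zone moves a little with the scale but does not close. With a true ratio of 1.6, the chance that the lower limit exceeds 1.4 is 30% (log scale, fixed reference). With a true ratio of 2.0 it is 91%.

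**4. Effect of an estimated reference (illustration only).** Suppose the reference were a group of 8 with the same CV of 0.4. On the log scale the half-width becomes t(0.95, 18) × 0.385 × √(1/12 + 1/8) = 1.734 × 0.385 × 0.456 = 0.305, a factor of 1.36. The undecided zone would then run from 1.4/1.357 = 1.03 to 1.4 × 1.357 = 1.90.

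**5. The 95% CI in SAP 2.4.** t(0.975, 11) = 2.201, so the width is 2 × 2.201 × 0.4/√12 = 50.8%. The 41.4% belongs to the 90% interval.

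**The case against.** The strongest defence is that the sentence is loose wording with no consequence. No output in Protocol 9.3.3 or SAP 6.2 applies a 40% criterion or forms a ratio to earlier data. The primary endpoint is safety, the tabulated precision is right, and the SAP has already dropped the sentence. All of that stands. It limits the weight of the point but does not make the sentence true.

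A second defence is that the study is quite informative about differences of this size, and that is also right. Against a fixed reference, a true ratio of 1.4 would be separated from no difference with 88% power on the log scale (94% for a 40% difference on the additive scale with constant SD). If exposure were truly equal, the interval would lie inside 0.6 to 1.4 with probability 0.88 (log scale, fixed reference). But separating a ratio from 1 is a different question from deciding whether the difference exceeds 40%, and the sentence claims the latter.

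Three stronger readings are tempting, and the documents do not support them.

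- A reader might infer that the study has no ability to address a 40% difference. The power figures above, and the observed ratios at which the interval does settle the matter, show otherwise.
- A reader might infer that the N=8 group in Table 1 is the reference, so that the relevant interval is much wider than 41.4%. Protocol 9.5 uses that group only for the CV. It received a single 100 mg dose, whereas this study gives 300 mg and then 150 mg QD, so raw exposures are not directly comparable.
- A reader might infer that the CV grid is inadequate, because the text says "Since we anticipate that study participants may experience more variability in PK parameters than the available data" and yet tabulates 0.2 and 0.3. The case that drives the sample size is 0.4, which is above the observed 0.33 to 0.38. The lower columns are additional scenarios, and the documents give no source for 0.5.

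**Conclusion.** The point holds as a fault in what Protocol 9.5 says the sample size can conclude. Full interval width has been read as a criterion for a difference, and nothing else in the section supports that criterion. Even with a perfectly known reference, observed ratios from about 1.16 to 1.77 (1.15 to 1.71 on the log scale), and from about 0.50 to 0.76 on the low side, leave the 40% question open.

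These limits assume n = 12, a realised CV of 0.4 and a two-sided 90% interval. A smaller CV narrows the zone, and uncertainty in the reference widens it. The finding does not touch Table 2, the choice of 12 per cohort or the planned descriptive analyses. The 95% label in SAP 2.4 is a separate small error attached to the same figures.

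**What to change.** In Protocol 9.5, delete the sentence about a difference above 40% and put in its place:

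> At CV 0.4 each cohort mean is estimated to within ±20.7% (90% CI); the sample size is not chosen to decide whether exposure differs by more than 40% from earlier data.

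In SAP 2.4, change the 95% CI in the sentence before Table 4 to a 90% CI, so that it matches the table.

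If the sponsor does want to compare exposure with earlier data, the plan would have to name the reference, the scale (including any dose normalisation) and the margin, and allow for uncertainty in the reference.

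The cost is one sentence in the protocol and one word in the SAP. Neither the sample size nor the CV columns need to change.

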**Table 2. Percentile Range and Width of 90% Confidence Intervals for the Mean PK Parameter**

N	CV=0.2		CV=0.3		CV=0.4	
	Range	Width	Range	Width	Range	Width
8	86.6-113.4%	26.8%	79.9-120.1%	40.2%	73.2-126.8%	53.6%
10	88.5-111.5%	23.1%	82.7-117.3%	34.6%	76.9-123.1%	46.2%
12	89.6-110.4%	20.7%	84.5-115.5%	31.1%	79.3-120.7%	41.4%
14	90.5-109.5%	19.0%	85.8-114.2%	28.4%	81.1 -119.0%	37.9%

## **10. SUPPORTING DOCUMENTATION AND OPERATIONAL CONSIDERATIONS**

### **10.1. Appendix 1: Regulatory, Ethical, and Study Oversight Considerations**

#### **10.1.1. Regulatory and Ethical Considerations**

This study will be conducted in accordance with the protocol and with the following:

- Consensus ethical principles derived from international guidelines, including the Declaration of Helsinki and CIOMS International Ethical Guidelines;
- Applicable ICH GCP guidelines;
- Applicable laws and regulations, including applicable privacy laws.

The protocol, protocol amendments, ICD, SRSD(s), and other relevant documents (eg, advertisements) must be reviewed and approved by the sponsor, submitted to an IRB/EC by the investigator, and reviewed and approved by the IRB/EC before the study is initiated.

Any amendments to the protocol will require IRB/EC approval before implementation of changes made to the study design, except for changes necessary to eliminate an immediate hazard to study participants.

Protocols and any substantial amendments to the protocol will require health authority approval prior to initiation except for changes necessary to eliminate an immediate hazard to study participants.

The investigator will be responsible for the following:

- Providing written summaries of the status of the study to the IRB/EC annually or more frequently in accordance with the requirements, policies, and procedures established by the IRB/EC;
- Notifying the IRB/EC of SAEs or other significant safety findings as required by IRB/EC procedures;
- Providing oversight of the conduct of the study at the site and adherence to requirements of 21 CFR, ICH GCP guidelines, the IRB/EC, European regulation 536/2014 for clinical studies, European Medical Device Regulation 2017/745 for clinical device research, and all other applicable local regulations.

#### **10.1.1.1. Reporting of Safety Issues and Serious Breaches of the Protocol or ICH GCP**

In the event of any prohibition or restriction imposed (ie, clinical hold) by an applicable regulatory authority in any area of the world, or if the investigator is aware of any new information that might influence the evaluation of the benefits and risks of the study intervention, Pfizer should be informed immediately.

In addition, the investigator will inform Pfizer immediately of any urgent safety measures taken by the investigator to protect the study participants against any immediate hazard, and of any serious breaches of this protocol or of the ICH GCP guidelines that the investigator becomes aware of.

#### **10.1.2. Financial Disclosure**

Investigators and sub-investigators will provide the sponsor with sufficient, accurate financial information as requested to allow the sponsor to submit complete and accurate financial certification or disclosure statements to the appropriate regulatory authorities. Investigators are responsible for providing information on financial interests during the course of the study and for 1 year after completion of the study.

#### **10.1.3. Informed Consent/Accent Process**

The investigator or the investigator's representative will explain the nature of the study, including the risks and benefits, to the participant or their legally authorized representative and answer all questions regarding the study. The participant or their legally authorized representative should be given sufficient time and opportunity to ask questions and to decide whether or not to participate in the trial.

Participants must be informed that their participation is voluntary. Participants or their legally authorized representative (if allowed by local regulations) will be required to sign a statement of informed consent that meets the requirements of 21 CFR 50, local regulations, ICH guidelines, privacy and data protection requirements, where applicable, and the IRB/EC or study center.

The investigator must ensure that each participant or their legally authorized representative is fully informed about the nature and objectives of the study, the sharing of data related to the study, and possible risks associated with participation, including the risks associated with the processing of the participant's personal data.

The participant or their legally authorized representative must be informed that their personal study-related data will be used by the sponsor in accordance with local data protection law. The level of disclosure must also be explained to the participant or their legally authorized representative.

The participant or their legally authorized representative must be informed that their medical records may be examined by Clinical Quality Assurance auditors or other authorized personnel appointed by the sponsor, by appropriate IRB/EC members, and by inspectors from regulatory authorities.

The investigator further must ensure that each study participant or their legally authorized representative is fully informed about their right to access and correct their personal data and to withdraw consent for the processing of their personal data.

The medical record must include a statement that written informed consent was obtained before the participant was enrolled in the study and the date on which the written consent was obtained. The authorized person obtaining the informed consent must also sign the ICD.

Participants or their legally authorized representative must be reconsented to the most current version of the IRB/EC-approved ICD(s) during their participation in the study as required per local regulations.

A copy of the ICD(s) must be provided to the participant or their legally authorized representative (if allowed by local regulations).

Participants who are rescreened are required to sign a new ICD.

#### **10.1.4. Data Protection**

All parties will comply with all applicable laws, including laws regarding the implementation of organizational and technical measures to ensure protection of participant data.

Participants' personal data will be stored at the study site in encrypted electronic and/or paper form and will be password protected to ensure that only authorized study staff have access. The study site will implement appropriate technical and organizational measures to ensure that the personal data can be recovered in the event of disaster. In the event of a potential personal data breach, the study site will be responsible for determining whether a personal data breach has in fact occurred and, if so, providing breach notifications as required by law.

To protect the rights and freedoms of participants with regard to the processing of personal data, participants will be assigned a single, participant-specific numerical code. Any participant records or data sets that are transferred to the sponsor will contain the numerical code; participant names will not be transferred. All other identifiable data transferred to the sponsor will be identified by this single, participant-specific code. The study site will maintain a confidential list of participants who participated in the study, linking each participant's numerical code to their actual identity and medical record ID. In case of data transfer, the sponsor will protect the confidentiality of participants' personal data consistent with the clinical study agreement and applicable privacy laws.

Information technology systems used to collect, process, and store study-related data are secured by technical and organizational security measures designed to protect such data against accidental or unlawful loss, alteration, or unauthorized disclosure or access.

The sponsor maintains standard operating procedures on how to respond in the event of unauthorized access, use, or disclosure of sponsor information or systems.

#### **10.1.5. Committees Structure**

##### **10.1.5.1. Data Monitoring Committee**

This study will use the program-level E-DMC which is independent of the study team and includes only external members, and is responsible for the ongoing monitoring of the

efficacy and safety of participants in the program's studies according to the E-DMC charter. This study is not assessing efficacy and assessing only safety. The E-DMC charter describes the role of the E-DMC in more detail for this study. The recommendations made by the E-DMC will be forwarded to the appropriate authorized Pfizer personnel for review and final decision as appropriate. Pfizer will communicate such decisions, which may include summaries of aggregate analyses of endpoint events of safety data, as well as those that are not endpoints, to regulatory authorities and investigators, as appropriate.

#### **10.1.6. Dissemination of Clinical Study Data**

Pfizer fulfills its commitment to publicly disclose clinical study results through posting the results of studies on [www.clinicaltrials.gov](http://www.clinicaltrials.gov) (ClinicalTrials.gov), the EudraCT/CTIS, and/or [www.pfizer.com](http://www.pfizer.com), and other public registries and websites in accordance with applicable local laws/regulations. In addition, Pfizer reports study results outside of the requirements of local laws/regulations pursuant to its SOPs.

In all cases, study results are reported by Pfizer in an objective, accurate, balanced, and complete manner and are reported regardless of the outcome of the study or the country in which the study was conducted.

